administrations. This criterion is necessary to permit selection of the necessary treatment and generalization probe items as described below, and will minimize ceiling effects on the naming probes. Fourth, in order to avoid enrolling into the study participants who have profound naming impairments and are therefore unlikely to benefit from the study treatment (e.g., patients with global aphasia and/or verbal output limited to recurrent stereotypy), all participants must obtain a CAT Naming modality T-score greater than or equal to 40. Finally, we will exclude from participation potential participants with severe motor speech disorder (i.e., apraxia of speech and/or dysarthria). Motor speech diagnosis and severity judgments will be made by study investigators with experience in this area ([name], [name], [name]), based on the following samples of behavior: Connected speech samples (described below); three recorded attempts at laryngeal diadochokinesis at slow, medium, and fast rates; three trials of maximum sustained phonation; and recorded responses to the three subtests of the Apraxia Battery for Adults-2, including Speech Diadochokinesis, Repetition of Words of Increasing Length, and Word Repetition with Repeated Trials. Two judges will independently diagnose and rate the severity of motor speech disorder in each potential participant. A third judge will provide a diagnosis and rating to resolve any disagreements regarding presence or severity of motor-speech disorders. Chart review of PIRATE participants to date suggests that the above additional five criteria would have excluded approximately 20% of the unique veterans served by the program. Thus, out of 72 patients who will be seen in PIRATE over the four-year duration of the project, approximately 58 should be eligible for enrollment in the study. Of these 58 eligible veterans, it is reasonable to expect that at least 50 will enroll in the study and complete the treatment and all study visits (including follow-up visits). This sample size should be sufficient for detecting the relationships between treatment response, psycholinguistic profile, and cognitive performance relevant to Specific Aim 1, and to detect differences relevant to testing the dose-response hypotheses in Specific Aim 2.

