hours. All treatment and probe pictures will be selected from the pictures named correctly on fewer than two of those occasions. Four sets of 10 items each will be selected as potential treatment items, along with four sets of 10 related generalization probe items and four sets of 10 unrelated generalization probe items. For each treatment item, a category coordinate will be selected as a generalization probe item. The unrelated generalization probes will be selected from remaining items belonging to categories not occurring within the treatment set. These items will also be selected to minimize associative and other semantic relationships with items in the treatment sets. Within the constraints of semantic relatedness and baseline performance level, we will balance the treatment and generalization sets for lexical frequency and length.

[figure not shown]

Figure 5. Panel A: Expected score for each of the seven 25-item PNT alternate forms, compared to empirical data of 254 aphasic patients. Panel B: Mean Rasch-scaled score for each of the seven alternate PNT forms, for a subsample of 57 aphasic patients.

C.2.2 Probe stimuli, procedures and schedule

Following baseline assessment of all 361 UCSD CRL items, the 40 items selected for training, 40 related items, and 40 unrelated items will be probed at treatment initiation, three times per week during

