Study measures will be subjected to two sets of analyses which test the dose-response hypotheses relevant to Specific Aim 2. These analyses will compare the PNT scores and acquisition and generalization probe scores across the 4 weeks of PIRATE treatment, to determine the dose-response relationship and to identify the points of largest change in response to treatment. The last of the three weekly naming probes will serve as a measure of weekly acquisition and generalization performance. This will ensure that performance on PNT and naming-probe measures may be directly compared, as they will be on the same schedule.

First, the data for the PNT scores and the acquisition/generalization probes will be analyzed with a multivariate mixed model with polynomial trend contrasts. To simplify interpretation, only time points 2 through 6 (program entry through program exit) will be included in the trend analyses. These trend analyses will first test whether there is a linear relationship between time in treatment and treatment response for study measures, as predicted by Hypothesis 2a. Second, they will test whether acquisition and generalization probes show additional curvilinear relationships to time in treatment, as predicted by Hypothesis 2b. We anticipate that there will be a positive linear trend between program entry and program exit for PNT scores and for acquisition and generalization probes. This finding would indicate that the four weeks of treatment results in significant score gains. We further predict that the trend for acquisition probes will also have a significant curvilinear (quadratic or higher-order) component, consistent with decelerating improvement across the four weeks of treatment. This finding would indicate that the largest gains for specifically treated skills/items occur early in treatment, with declining gains in later weeks. Finally, we predict that the generalization probes will also demonstrate a curvilinear relationship to time, due to accelerating improvement across the four week program. This finding would indicate that the largest gains for related but untreated items occur late in treatment, emerging later than the gains for specifically treated forms.

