Second, six pairwise planned comparisons of scores across all seven consecutive measurement intervals will be carried out, using Bonferroni-corrected t-tests to maintain the familywise type-I error rate at 0.1. As predicted by Hypothesis 2a and consistent with the preliminary outcome data from PIRATE (see B.1.3 above), we anticipate that there will be a significant increase in both PNT score and acquisition/generalization probe performance for each additional one-week increment of treatment. We also predict non-significant changes between the initial evaluation and program entry and between program exit and follow-up.

In case a linear relationship is not found between time in treatment and outcome measures, additional analyses will be carried out examining the performance of different subsets of veterans. For example, veterans will be divided into groups based on their aphasia severity, since previous treatment findings have suggested that milder aphasia severity may be associated with less change on language-performance measures^[1]. Separate trend analyses will be carried out for the different severity groups, to examine whether different dose-response relationships may be observed for different aphasia groups.

In addition to these within-participant analyses examining dose-response relationships, a complementary set of between-participants analyses will be carried out, examining the effects of two versus four weeks of treatment for different randomly-selected groups of participants. It is standard practice in the dose-response literature to compare the response of groups exposed to different amounts of a therapeutic

agent, to see the incidence of positive or negative responses to the agent in the groups (e.g., frequency of remission or toxicity^[110]). These complementary between-participant analyses will simulate this comparison for the current study, providing an additional randomized-control measure of the effect of high dosage SFA on individuals with naming impairments. For these analyses, participants will be randomized to one of two groups. For half the participants, outcome measures (naming and PNT scores) will be sampled after two weeks' exposure, while for the other half, outcome measures will be sampled after the full four weeks of treatment. We anticipate that changes in study measures will be larger for the four-week group than for the two-week group.

C.3.3 Additional analyses of general language performance and connected speech

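### Within each measure, the six weekly-interval t-tests should use Holm rather than Bonferroni, and the plan should say that the familywise 0.1 applies per measure

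*Combined protocol and SAP*

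**What the plan says.** Section C.3.2 first fits a trend model and then plans that "six pairwise planned comparisons of scores across all seven consecutive measurement intervals will be carried out". The error control for this set of tests is described as "using Bonferroni-corrected t-tests to maintain the familywise type-I error rate at 0.1". The scope is several outcomes: "These analyses will compare the PNT scores and acquisition and generalization probe scores across the 4 weeks of PIRATE treatment".

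The predictions attached to the six contrasts are of two kinds. For the four treatment weeks, the plan expects that "there will be a significant increase in both PNT score and acquisition/generalization probe performance for each additional one-week increment of treatment". For the other two intervals it says: "We also predict non-significant changes between the initial evaluation and program entry and between program exit and follow-up".

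C.3.2 does not say whether the 0.1 is held within each measure or across all of them. It gives no other multiplicity control across measures, and it does not say whether the t-tests are one- or two-sided.

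**The concern.** There are two separate issues.

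The first is what the 0.1 covers. The only count attached to the family is six, and six contrasts is what one measure yields. With three measures there are 18 tests. A reader told that the familywise rate is 0.1 may take it to cover every weekly finding in the dose-response section. On the per-measure reading it does not. This matters because C.3.2 also aims to locate where in the four weeks the change is largest, which means reading individual weeks and measures.

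The second is power. The pairwise part of Hypothesis 2a needs four significant results out of six on each measure. Bonferroni holds every test at the strictest threshold, however many others have already been rejected. Holm controls the same error rate under the same conditions and never rejects fewer hypotheses.

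**Working it through.** **Inputs from the plan**
- Familywise rate 0.1, Bonferroni, six contrasts (C.3.2). Seven measurement points give six intervals, so the reference to seven intervals is a wording slip.
- Three measures: PNT, acquisition, generalization (C.3.2).
- Sample size: "at least 50 will enroll in the study and complete the treatment and all study visits" (C.1).

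**Assumptions, because the documents are silent**
- Two-sided tests.
- Equal, independent errors at the seven points, so adjacent differences correlate at -0.5.
- Between-measure correlation from 0 to 0.9.
- Weekly gain expressed in SD units of the weekly difference.

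**1. The plan's own figure.** Per-test level 0.1/6 = 0.0167, and 6 × 0.0167 = 0.10. This reproduces the stated rate for one measure. With six independent tests the exact rate is 1 − (1 − 0.0167)^6 = 0.096.

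**2. Three measures, each at 0.1, no true change anywhere**
- Three independent families at exactly 0.1: 1 − 0.9^3 = 0.27.
- 18 independent tests: 1 − (1 − 0.0167)^18 = 0.26.
- Simulated paired t-tests, n = 50:

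| Between-measure correlation | Chance of at least one false rejection |
|---|---|
| 0 | 0.24 |
| 0.5 | 0.22 to 0.23 |
| 0.7 | 0.20 |
| 0.9 | 0.15 |

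The range is therefore 0.15 to 0.27. C.2.2 schedules the PNT weekly in the baseline and treatment phases and does not clearly include follow-up. Without that PNT contrast there are 17 tests, and 1 − (1 − 0.0167)^17 = 0.25, so little changes.

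**3. Three measures, some change real (independence)**
- Every weekly gain real on every measure: 3 × 2 = 6 true nulls remain, and 1 − (1 − 0.0167)^6 = 0.096.
- Only treated items gain: 2 + 6 + 6 = 14 true nulls remain, and 1 − (1 − 0.0167)^14 = 0.21.

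**4. Holm against Bonferroni within one measure.** Holm orders the six p-values and compares them in turn with 0.1/6, 0.1/5, 0.1/4, 0.1/3, 0.1/2 and 0.1/1 (0.0167, 0.0200, 0.0250, 0.0333, 0.0500, 0.1000), stopping at the first failure. Bonferroni uses 0.0167 throughout. Simulation with n = 50, four equal real weekly gains and two true nulls:

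| Assumed weekly gain (SD of difference) | Average power per weekly contrast, Bonferroni → Holm | All four significant, Bonferroni → Holm | Any false rejection, Bonferroni → Holm |
|---|---|---|---|
| 0.3 | 0.37 → 0.40 | 0.001 → 0.007 | 0.035 → 0.048 |
| 0.4 | 0.64 → 0.71 | 0.08 → 0.21 | 0.034 → 0.063 |
| 0.5 | 0.85 → 0.90 | 0.48 → 0.66 | 0.031 → 0.083 |
| 0.6 | 0.96 → 0.98 | 0.84 → 0.92 | 0.033 → 0.096 |

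Holm stays at or below 0.1 in every row.

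**The case against.** The plan does not state that the family is per measure. If "Bonferroni-corrected t-tests" was meant to span all 18 tests, at 0.1/18 = 0.0056 each, the rate is held. This stands: the inflation is conditional on a reading that the text suggests but does not fix.

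The pairwise prediction is joint. A claim made only if every measure gains in every week is not inflated by adding measures. C.3.2 also tests Hypothesis 2a first through the linear trend, with the t-tests second. Both points stand. They confine the inflation to isolated weekly or single-measure claims.

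The 0.15 to 0.27 assumes that treatment changes nothing on any measure. If all weekly gains are real the figure is about 0.10. This also stands, although gains confined to treated items, a pattern that the background sections take seriously, give 0.21 under independence.

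A reader might go further and infer a rate as high as 0.34, from four measures (1 − 0.9^4). C.2.1 does define two untreated sets, "along with four sets of 10 related generalization probe items and four sets of 10 unrelated generalization probe items", but C.3.2 describes the expected generalization gains as gains on related untreated items and never names the unrelated set as a separately tested measure. The documents do not support that figure.

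A reader might also infer that 0.1 is an error, or that the two no-change contrasts do not belong in the family. The 0.1 is disclosed and is a choice. A six-test family that includes the stability contrasts is valid, and dropping them would move the Bonferroni threshold only from 0.0167 to 0.1/4 = 0.025.

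**Conclusion.** The point holds in a limited form. Bonferroni is valid here, but Holm does at least as well at the same level on the same tests. For the four-week pattern that Hypothesis 2a predicts, the gain is large at middling effects: 0.08 to 0.21 at 0.4 SD and 0.48 to 0.66 at 0.5 SD. The plan gives no weekly effect size, so these are illustrations; the gain is negligible at 0.3 SD, where neither method has a realistic chance of finding all four.

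On the error rate, the plan's 0.1 is correct for one measure. Across three measures on the per-measure reading it is about 0.15 to 0.27 with no true change, and about 0.10 if every weekly gain is real. It would be wrong to call any of these the trial's actual error rate, because the family is undefined and the between-measure correlation is not given. The joint every-measure, every-week claim is unaffected.

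**What to change.** In C.3.2, replace Bonferroni with Holm for the six contrasts, keeping the level at 0.1. Add that the 0.1 is held separately for each measure, so that an isolated single-week or single-measure result is not reported as carrying a 10% error rate across measures. This takes a sentence or two and no new data.

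Costs:
- Holm has no simple matching simultaneous confidence intervals. If Bonferroni intervals are shown alongside, they can disagree with the Holm decision near the threshold.
- Holm uses error that Bonferroni leaves unspent. At a 0.5 SD weekly gain, the chance of a false rejection among the two stability contrasts rises from 0.031 to 0.083 per measure. Over three independent measures that is 1 − 0.969^3 = 0.09 against 1 − 0.917^3 = 0.23. The per-measure statement is therefore needed together with Holm; Holm alone does not address the gap across measures.

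Lowering the level to 0.05, widening the family to all measures, or removing the stability contrasts are optional trade-offs and not part of this fix. For example, Holm over the four weekly contrasts on three measures at 0.05 starts at 0.05/12 = 0.0042 rather than 0.0167, which can cost weekly power.

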There was significant improvement from initial evaluation to program entry ($F[1,40] = 6.042$, $MSE = 0.014$, $p = 0.018$, $\eta_p^2 = 0.131$) and relatively greater improvement between program entry and program exit ($F[1,40] = 53.168$, $MSE = 0.013$, $p < 0.001$, $\eta_p^2 = 0.571$). The observed pattern of minimal change across the baseline interval coupled with significant improvement across the treatment interval supports the effectiveness of PIRATE in treating aphasia. In addition, these changes on this broad measure of language performance likely underestimate the magnitude of treatment-related changes in the proposed research. The PICA samples communicative functioning at a broad level, encompassing performance not only in targeted domains (such as naming)

[figure not shown]

Figure 1. Mean PICA z-scores for n=35 patients with complete data available at three assessment points. Error bars indicate +/- 1 standard error.

but also in domains not targeted in therapy, which are unlikely to show improvement. The language performance assessments to be used in the proposed research measure performance on naming behaviors which are the object of treatment, rather than a broad index of both treated and untreated behaviors. Consequently, we may expect that the intensive delivery schedule followed in PIRATE and in the proposed research will result in even larger gains on study measures than those described here.

B.1.3 Analysis of Preliminary Data 2: Dose-Response Relationship

As noted above, the first six PIRATE sessions were three weeks in length, and the remaining sessions have been four weeks in length. Comparison of outcomes between groups receiving 3 versus 4 weeks of treatment permitted us to estimate the marginal benefit of an additional week of intensive aphasia treatment in terms of a broad performance-based outcome. To derive these estimates, we conducted ANCOVAs on the PICA overall z-scores, with the post-treatment scores as the dependent variable, treatment group (3-week vs. 4-week) as the independent variable, and pre-treatment scores collected at program entry as the covariate.

For the PICA, data at program entry and program exit were available for 15 veterans who received three weeks of treatment and 27 veterans who received four weeks. The demographic and clinical characteristics of each group are presented in Table 2.

	3-Week Group (n=15)	4-Week Group (n=27)
Months Post Onset at Program Entry, Median (IQR)	19 (38)	21 (31)

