The following procedures will be implemented to monitor and ensure treatment fidelity. All treatment sessions will be video recorded. For each participant and each day of treatment, study staff not providing treatment will randomly select 15 minutes (~ 7% of total treatment time) of video and review it for adherence to the semantic feature analysis (SFA) protocol. All deviations will be discussed with the treating clinicians. Monitoring will occur and feedback will be provided to clinicians by the end of the business day following the monitored sessions. When monitoring of a given clinician-participant pair detects no more than one deviation on three consecutive days, the pair will be monitored weekly for the remainder of the 4-week session. If subsequent weekly monitoring reveals more than one deviation from the SFA protocol, daily monitoring will be re-instituted until the criterion for weekly monitoring is again reached.

Treatment and probe stimuli for study participants will consist of picturable nouns, consistent with methods used in existing SFA treatment studies. All pictures used as treatment and probe stimuli will be drawn from a subset of 361 of the 520 object pictures published by the UCSD Center for Research in Language International Picture Naming Project^[91]. These 361 pictures were selected by removing from the full set 159 picture stimuli that are also included in the Philadelphia Naming Test^[92], which will serve as a secondary outcome measure for Specific Aims 1 and 2. Participants will be asked to name this set of 361 pictures on three occasions across the two days of their initial evaluation, with all administrations separated by at least 5

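### For the naming probes, item selection biases the initial-evaluation-to-entry comparison upward, so it cannot test for a stable baseline

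*Combined protocol and SAP*

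**What the plan says.** Section C.2.1 (Treatment) sets out how the probe items are found: "Participants will be asked to name this set of 361 pictures on three occasions across the two days of their initial evaluation". It then gives the rule: "All treatment and probe pictures will be selected from the pictures named correctly on fewer than two of those occasions". This covers the treated, related and unrelated sets alike.

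Section C.2.2 gives the next measurement of the chosen sets: "the 40 items selected for training, 40 related items, and 40 unrelated items will be probed at treatment initiation", then three times weekly, at exit and at follow-up. Figure 4, the schedule of procedures, is not available. The text describes no other initial-evaluation score for the chosen items and no fresh probe of them between selection and entry. Section C.2 puts the initial evaluation 4 to 6 weeks before entry.

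Section C.3.2 plans "six pairwise planned comparisons of scores across all seven consecutive measurement intervals" with Bonferroni correction to a familywise error of 0.1. It expects that "there will be a significant increase in both PNT score and acquisition/generalization probe performance" for each added week of treatment, and continues: "We also predict non-significant changes between the initial evaluation and program entry and between program exit and follow-up". The same section puts the PNT and the weekly naming-probe measure on one schedule. For the trend analyses it specifies that "only time points 2 through 6 (program entry through program exit) will be included in the trend analyses".

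**The concern.** Items that enter the probe sets because they were failed at the initial evaluation have initial-evaluation scores that are low partly by chance. A new naming of the same items at entry loses that chance component, so the score is expected to rise even if nothing has changed in the participant.

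A rise on the probes before treatment could then be misread as a practice effect or an unstable baseline. A flat result would be no more reassuring, since it could hide a real decline over the 4 to 6 weeks. The protocol attaches evidential weight to this interval: in its own pilot data (B.1.2), it says that "minimal change across the baseline interval coupled with significant improvement across the treatment interval supports the effectiveness of PIRATE".

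**Working it through.** The plan gives no expected change, standard deviation or power for this comparison, so there is no figure to reproduce. The check asks how large the rise is when true ability does not change.

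**Inputs from the documents.** 361 pictures, each named three times, with items kept if correct 0 or 1 times (C.2.1). At least 120 such items per participant, and 50 completers (C.1). 40 items per set (C.2.2). Familywise alpha 0.1 over six comparisons (C.3.2), so 0.1/6 = 0.0167 per test, taken as two-sided. The wording counts six comparisons but seven intervals. Seven time points give six intervals, and 0.1/7 = 0.0143 would not change the conclusion.

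**Step 1: direction, for a single item.** Let an item have a fixed naming probability p. Given selection, its expected initial-evaluation score is

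E[X/3 | X ≤ 1] = p(1−p)² / [(1−p)³ + 3p(1−p)²] = p/(1+2p).

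At entry it is p. The expected rise is p − p/(1+2p) = 2p²/(1+2p), which is positive for any item that is sometimes named and sometimes missed. At p = 0.2 it is 0.08/1.4 = 5.7 points, and at p = 0.5 it is 0.5/2 = 25 points. Using only the third naming as the baseline gives the same expectation, p/(1+2p), with more noise. The direction therefore needs no distributional assumption. The rise vanishes only if every item is always or never named.

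**Step 2: size, when items differ.** *Assumption:* item probabilities follow a Beta distribution with mean m and concentration c, where a = mc and b = (1−m)c. Small c means items are close to all-or-none. Then

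- P₀ = b(b+1)(b+2) / [c(c+1)(c+2)]
- P₁ = 3ab(b+1) / [c(c+1)(c+2)]
- initial score = (P₁/3) / (P₀+P₁)
- entry score = [P₀a + P₁(a+1)] / [(c+3)(P₀+P₁)]

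Example, m = 0.5 and c = 1: P₀ = 1.875/6 = 0.3125 and P₁ = 1.125/6 = 0.1875. Initial score = 0.0625/0.5 = 0.125. Entry score = (0.15625 + 0.28125)/(4 × 0.5) = 0.219. The rise is 9.4 points.

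**Step 3: how often it is significant.** Simulation with 361 items, at least 120 eligible, 40 drawn, 50 participants, no true change, a one-sample t-test on the differences at 0.0167, and 400 trials per cell (Monte Carlo standard error at most 2.5 points).

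| Mean | Concentration | Initial | Entry | Rise (points) | Significant: mean of three / last naming only |
|---|---|---|---|---|---|
| 0.3 | 0.3 | 3.6% | 6.0% | 2.4 | 99.8% / 91.5% |
| 0.5 | 1 | 12.5% | 21.9% | 9.4 | in range below |
| 0.5 | 2 | 16.7% | 30.0% | 13.3 | in range below |
| 0.3 | 0.1 | 1.4% | 2.3% | 0.9 | 73.8% / 48.2% |
| 0.5 | 0.1 | 2.3% | 3.8% | 1.5 | 94.8% / 77.7% |
| 0.1 | 0.3 | 1.3% | 2.1% | 0.8 | 60.5% / 40.0% |
| 0.1 | 0.1 | 0.5% | 0.8% | 0.3 | 20.0% / 17.0% |

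Over means 0.3 to 0.5 and concentrations 0.3 to 2, the share significant is 99.8% to 100% with the mean of three namings and 92% to 100% with the last alone. In items, 2.4 to 13.3 points is 0.024 × 40 = 1.0 to 0.133 × 40 = 5.3 of 40.

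**Step 4: control.** In a second simulation, participants' mean accuracy varied from 0.1 to 0.6. Items drawn without regard to baseline performance gave a significant result in about 1% to 3% of trials, against a nominal 1.7%. Selected items gave 54% to 78% at concentration 0.1, 89% to 99% at 0.2, and 99.5% to 100% at 0.5 or more. The selection rule is therefore the cause.

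**The case against.** The strongest reply is that the comparison is partly inferred. The documents never state that the selection namings are the first probe score, the sentence predicting no change names no outcome, and Figure 4 is not available. On that reading, only the PNT has an initial-evaluation value and no biased probe test exists. The condition stands, and the finding is stated with it. The reading itself is hard to hold, because C.3.2 puts the probes and the PNT on one schedule and runs its comparisons over all seven points without exempting the probes. If it were right, the plan would still need to say so, and the same wording change would do it.

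Second, little hangs on this test. No decision rule uses it, and a false rise contradicts the investigators' own prediction, so it does not inflate a treatment claim. The pilot interpretation in B.1.2 concerns the PICA, not naming probes. The plan also has other measures before treatment: the PNT, nonword repetition, the CAT, connected speech and the randomized delayed week. All of this limits the harm. It does not make the planned probe comparison valid.

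Third, the size depends on an assumed distribution and can be under one item in 40. That is true. But even in the weakest case tabulated, the test rejects in 17% to 20% of trials, about ten times its nominal level.

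**Conclusion.** The concern holds. With the selection namings as the first time point, the naming-probe comparison from initial evaluation to entry is biased upward and says nothing reliable about baseline stability. The direction follows from the selection rule. The size depends on item consistency, which the documents do not report: 2.4 to 13.3 points under the main Beta assumptions, and 0.3 to 1.5 points if items are nearly all-or-none or accuracy is very low.

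The damage is confined to this one comparison. The trend analyses over time points 2 to 6, the Aim 1 entry-to-exit change score, the weekly treatment comparisons and exit to follow-up all start from fresh probes, and PNT items are not selected on the participant's failures. The plan should be corrected, but its main conclusions are not threatened by this point.

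**What to change.** In C.3.2, start the naming-probe series at the program-entry probe and drop the comparison from initial evaluation to entry for these measures. Five comparisons remain, so the Bonferroni level for them is 0.1/5 = 0.02.

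Judge stability over that interval on the PNT. C.2.3 has each participant receive 50 PNT items by program entry, consistent with two of the 25-item forms. Report the change with a confidence interval rather than treating non-significance as evidence of no change. The delayed group's pre-treatment week can serve as supporting evidence only if the existing schedule takes naming probes both at arrival and at the start of treatment.

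The cost is SAP wording only, with no new assessment. One probe comparison is lost, but it could not be interpreted as a stability check. The PNT interval may be wide, since it rests on 25-item forms.
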